### **12.3 Sample Size**

Twenty participants will be randomized to 2 groups (10 for each group), receiving either SXC-2023 or placebo treatment for 7 days. Study participants who complete all five cocaine infusion sessions will be considered completed participants. This study requires 8 completed participants in each group. It is expected that, if 20 participants are randomized, there should be at least 8 completers in each group.

### **12.4 Safety Data Analyses**

#### **12.4.1 Adverse Events (AEs)**

AEs will be coded using the most recent version of the Medical Dictionary for Regulatory Activities (MedDRA) preferred terms and will be grouped by system, organ, class (SOC) designation. The severity, frequency, and relationship of AEs to study drug will be presented by preferred term by SOC grouping. Listings of each individual AE including start date, stop date, severity, relationship, outcome, and duration will be provided.

#### **12.4.2 Vital Signs and ECG Changes**

Vital signs data (HR and BP) will be presented as summary statistics of maximum (max) absolute values, max change from baseline, and time to max value during the 1-hour period after each cocaine infusion. Data will be compared between groups and within groups by study day by Wilcoxon rank sum statistic. Effects will be considered statistically significant at a two-sided  $p < 0.05$ . In addition, summary statistics for vital signs at each study time point will also be presented. Changes in ECG intervals during saline infusion as compared to those taken during cocaine infusions will be reported as summary statistics. Clinically significant ECG changes will be presented as counts and percentages.

#### **12.4.3 Clinical Laboratory Parameters**

The concentrations of each clinical chemistry test will be presented for each group as n, mean, SD, median, minimum and maximum values at each scheduled assessment, as well as change from screening. The number of excursions outside the normal laboratory limits will be presented.

### **12.5 PK Data Analyses**

The following PK parameters will be determined for cocaine, BE, and SXC-2023 (as appropriate): maximum plasma concentration ( $C_{\max}$ ), area under the concentration-time curve (AUC) from time 0 to time t ( $AUC_{0-t}$ ), AUC from time 0 to 12 hours post-dose ( $AUC_{0-12}$ ), AUC from time 0 to time infinity ( $AUC_{0-\infty}$ ), time to maximum plasma concentration ( $T_{\max}$ ), trough

plasma concentration ( $C_{\text{trough}}$ ), terminal rate constant ( $\lambda_z$ ), half-life ( $t_{1/2}$ ), clearance (CL) and clearance from plasma after oral administration (CL/F). Weight-adjusted parameters may be determined when necessary.

#### **12.5.1 Parameters and Definitions**

PK parameters for plasma cocaine and BE as shown in [Table 5](#) will be calculated using noncompartmental methods.

**Table 5: Pharmacokinetic Parameters for Plasma Cocaine and BE**

PK Parameter	Definition
$C_{\max}$	Maximum observed plasma concentration
$t_{\max}$	Time of the maximum observed plasma concentration
$AUC_{(0-t)}$	Area under the plasma concentration-time curve from time 0 to the time (t) of last quantifiable concentration ( $C_t$ ) calculated by the linear-up/log-down trapezoidal rule
$AUC_{(0-\infty)}$	Area under the plasma concentration-time curve from time 0 extrapolated to infinity. The terminal area from $C_t$ to infinity was calculated by using the approximation as $C_t / \lambda_z$ thus $AUC_{(0-\infty)} = AUC_{(0-t)} + C_t / \lambda_z$
$AUC_{(0-12)}$	Area under the plasma concentration-time curve from time 0 to 12 hours post-dose
$AUC\%_{\text{extrap}}$	Percent of $AUC_{0-\infty}$ extrapolated from $C_t$ to infinity
$\lambda_z$	The terminal-phase exponential rate constant as calculated from the negative slope of the regression line for the terminal linear portion of the LN transformed plasma concentration versus time curve
$t_{1/2}$	The apparent terminal exponential half-life, calculated as $\ln(2) / \lambda_z$
CL	Total body clearance estimated as the drug dose divided by the plasma $AUC_{0-\infty}$ (cocaine only)
$C_{\max} * BW / 70 \text{ kg}$	$C_{\max}$ for a 40 mg dose of cocaine normalized to 70 kg body weight
$AUC_{0-t} * BW / 70 \text{ kg}$	$AUC_{0-t}$ for a 40 mg dose of cocaine normalized to 70 kg body weight
$AUC_{0-\infty} * BW / 70$	$AUC_{0-\infty}$ for a 40 mg dose of cocaine normalized to 70 kg body weight
$CL / BW * 70 \text{ kg}$	Clearance for a 40 mg dose of cocaine normalized to 70 kg total body weight (cocaine only)

Plasma concentration-time profiles of SXC-2023 on Day 9 (40 mg cocaine + saline infusion session) will be analyzed to obtain PK parameter estimates for SXC-2023 as shown in [Table 6](#).

**Table 6: Pharmacokinetic Parameters for Plasma SXC-2023**

PK Parameter	Definition
$C_{\max}$	Maximum observed plasma concentration
$T_{\max}$	Time of the maximum observed plasma concentration
$AUC_{(0-12)}$	Area under the plasma concentration-time curve from time 0 to 12 hours post-dose.
$\lambda_z$	The terminal-phase exponential rate constant as calculated from the negative slope of the regression line for the terminal linear portion of the LN transformed plasma concentration versus time curve. A minimum of 3 time points are required to calculate $\lambda_z$ .
$t_{1/2}$	The apparent terminal exponential half-life, calculated as $\ln(2)/\lambda_z$
$C_{\text{trough}}$	Trough (predose) concentration
CL/F	Apparent oral clearance estimated as the drug dose divided by the plasma $AUC_{(0-12)}$ at steady-state (of Day 10)
$C_{\max} * BW / 70 \text{ kg}$	$C_{\max}$ normalized to 70 mg body weight
$AUC_{(0-1t)} * BW / 70 \text{ kg}$	$AUC_{0-t}$ normalized to 70 mg body weight
$AUC_{(0-\infty)} * BW / 70 \text{ kg}$	$AUC_{0-\infty}$ normalized to 70 mg body weight
CL/F/ BW*70 kg	CL/F normalized to 70 kg total body weight

### 12.5.2 Statistical Analysis of PK Parameters

Plasma concentration-time profiles of cocaine and BE after infusion Sessions 3 and 5 will be analyzed to obtain PK parameter estimates and will be presented by participant and group summary statistics [N, mean, standard deviation (SD), % coefficient of variation (CV), median, minimum, maximum, geometric mean, CV% of geometric mean, and 90% confidence intervals (CI)].

Plasma concentration-time profiles of SXC-2023 on Day 9 (40 mg cocaine + saline infusion session) will be analyzed to obtain PK parameter estimates.

Individual participant and group summary statistics will be presented.

To assess the effect of SXC-2023 on the PK of cocaine and BE, an analysis of variance (ANOVA) will be performed on the natural logarithms (LN) of  $AUC_{0-t}$ ,  $AUC_{0-\infty}$  and CL, with treatment group as a fixed effect. In addition, an analysis may be conducted with the LN of 70 kg weight adjusted parameters [ $C_{\max} * \text{bodyweight (BW)} / 70 \text{ kg}$ ,  $AUC_{0-t} * BW / 70 \text{ kg}$ ,  $AUC_{0-\infty} * BW / 70 \text{ kg}$ , and  $CL / BW * 70 \text{ kg}$ ] when necessary. Within this ANOVA framework, comparisons of SXC-2023 versus placebo groups will be performed for baseline (Day 2), and Day 9 cocaine

challenge sessions (40 mg). The effect of saline/cocaine versus cocaine/saline randomized administration sequence will also be examined. The 90% CI for the ratio of the least squares means of SXC-2023 versus placebo AUC and  $C_{\max}$  parameters will be determined. The 90% CI will be obtained by exponentiation of the 90% confidence intervals for the difference between the least squares means on the LN scale.

## **12.6 Subjective Assessment Analyses (VAS and BSCS)**

Subjective effects VAS will be presented as summary statistics of maximum absolute values, maximum change from baseline, and time to maximum value over the 1-hour period after cocaine infusions. Data will be compared between groups and within groups between study days by Wilcoxon rank sum statistic.

BSCS scores will be presented for each item as n, mean, SD, median, minimum, and maximum values at each scheduled assessment. Group scores will be compared using Wilcoxon rank sum statistic for pre- and post- cocaine infusion assessments.

## **12.7 Missing Data**

Missing data will not be imputed for any analysis. The numbers of data points reflected in summary statistics will be indicated by presenting the number of observations.

# **13 DATA MANAGEMENT AND CASE REPORT FORMS**

## **13.1 Data Collection**

Data will be collected at the study sites on source documents, which will be transcribed at the site into case report forms (CRFs). The CRFs will be supplied by the Data Management Center. CRFs are to be completed on an ongoing basis during the study. The medical chart and the source documents are the source of verification of data. Completed CRFs will be collected by clinical monitors after monitoring against the source documents on a regular basis throughout the trial. The Investigator is responsible for maintaining accurate, complete and up-to-date records for each participant. The Investigator is also responsible for maintaining any source documentation related to the study, including clinical laboratory data, ECG tracings, *etc.*

## **13.2 Case Report Form Completion**

Electronic CRFs (eCRFs) will be provided for each participant. The participant identifiers and actual date (and time, if applicable) of each assessment should always be entered in the eCRFs. The final, completed eCRF for each participant must be signed and dated by the Investigator on the appropriate CRF page to signify that he/she has reviewed the report and certifies it to be complete and accurate.

### **13.3 Data Editing and Control**

Automated edit checks for missing, discrepant, and out-of-range data will be programmed into the study electronic data capture system (EDC). The identified discrepancies will be presented to the site user for resolution or justification. A TRI Data Manager will review the justification for all unresolvable discrepancies and will close or re-query them. Once all discrepancies and queries have been resolved, the PI will review the eCRFs in the EDC and confirm their accuracy with his/her electronic signature.

### **13.4 Data Monitoring**

The PI agrees to routine data audits by the sponsor's designated Site Monitors. Monitors will periodically visit the site to assure that data entered in the EDC are in agreement with source documents. Monitor reviews may also be accomplished remotely (off-site), by comparing EDC data with de-identified source documents submitted by the site for this purpose. Any inconsistencies will be resolved, and any changes to the data forms will be made using the procedures specified in the Study Operations Manual.

### **13.5 Data Processing**

A database will be constructed from the eCRFs that captures each item of data from each eCRF. All eCRFs will undergo a single-data entry process into the main study database with 100% quality control verification of all data entered into the eCRF. After entry, the data will be validated both manually and electronically. The database will undergo 100% quality assurance audit before locking and release for statistical analysis.

All AE information will be entered into the main study database from the AE CRF. AEs will be coded using the most recent version of the Medical Dictionary for Regulatory Activities (MedDRA) preferred terms and will be grouped by system, organ, class (SOC) designation. The severity, frequency, and relationship of AEs to study drug will be presented by preferred term by SOC grouping. Listings of each individual AE including start date, stop date, severity, relationship, outcome, and duration will be provided.

### **13.6 Study Documentation and Records Retention**

Study documentation includes all eCRFs, data correction forms (if used), workbooks, source documents, monitoring logs and appointment schedules, sponsor-investigator correspondence and regulatory documents (*e.g.*, signed protocol and amendments, IRB correspondence and approved consent form, signed ICFs, Statement of Investigator form, and clinical supplies receipts and distribution records).

Source documents include recordings of observations or notations of clinical activities and all reports and records necessary for the evaluation and reconstruction of the clinical research study. Accordingly, source documents include, if applicable, but are not limited to, laboratory reports, ECG tracings, X-rays, radiologist reports, patient diaries, biopsy reports, ultrasound photographs,

patient progress notes, charts or pharmacy records, and any other similar reports or records of any procedure performed in accordance with the protocol.

Whenever possible, the original recording of an observation should be retained as the source document; however, a photocopy is acceptable provided that it is a clear, legible, and an exact duplication of the original document.

FDA regulations require that the investigator must retain all study documentation pertaining to the conduct of a clinical trial. These documents must be kept for a minimum of two years after discontinuation of the IND or 2 years after the approval of a New Drug Application and finalization of all marketing strategies. In all instances, permission must be obtained from NIDA prior to disposition of any study documentation and materials.

### **13.7 Confidentiality**

#### **13.7.1 Confidentiality of Data**

Particular attention is drawn to the regulations promulgated by the FDA under the Freedom of Information Act providing, in part, that proprietary information furnished to clinical Investigators and IRBs will be kept confidential by the FDA only if maintained in confidence by the clinical Investigator and IRB.

By signing this protocol, the Investigator affirms to NIDA that information furnished to the Investigator by NIDA will be maintained in confidence and such information will be divulged to the IRB, expert committee; affiliated institution; and employees only under an appropriate understanding of confidentiality with such board or committee, affiliated institution and employees.

#### **13.7.2 Confidentiality of Records**

To maintain participant confidentiality, all laboratory specimens, CRFs, reports and other records will be identified only by a coded study participant identification number. Research and clinical records will be stored securely. Only research staff and sponsor or sponsor's representative will have access to the records. Participant information will not be released without written permission, except as necessary for monitoring by the FDA, sponsor, or sponsor's representative. Release of personal health information will be in accordance with current Standards for Privacy of Individually Identifiable Health Information (45 CFR parts 160 and 164) of the Health Insurance Portability and Accountability Act (HIPAA).

By signing the protocol, the PI also agrees that within local regulatory restrictions and ethical considerations, the sponsor, sponsor representative, or any regulatory agency may consult and/or copy study documents in order to verify CRF data.

## APPENDIX A: Schedule and Volume of Blood Sample Collections

**Table 7: Schedule and Volume of Blood Collections**

	Per sample		Study Day															Total Volume (mL)
			-28 to -4	-3	-2	-1	1	2	3	4	5	6	7	8	9	10	11	
Chemistries (including pregnancy testing and FSH, if needed)	5 mL	S	1	1							1					1		15
Hematology	4 mL	P	1	1							1					1		12
PK Samples for cocaine*	4 mL	P						13							13			104
PK Samples for SXC-2023*	4 mL	P													9	2 †	1 ††	48
Total (mL)			9	9				52				9			88	8	13	188
S = Serum, P = Plasma Additional 1 mL of blood will be added to every in-house collection as potential waste due to use of catheter. *For collection, storage, and shipping of PK samples see the study Manual of Procedures (MOP). † 24 and 36 hours after SXC-2023 dosing on Day 9 †† 48 hours after SXC-2023 dosing on Day 9																		

### Blood Drawing Procedure:

Blood drawn from all participants should be considered infectious and extreme caution should be used to avoid needle sticks and direct contact with blood or plasma.

Blood drawn for safety labs will be handled according to the procedures of the treating site and local analytical laboratory.

Blood drawn for plasma PK analysis will be handled as described in the study MOP. Plasma samples will be divided into two aliquots (one main and one backup).

## APPENDIX B: Instructions for Evaluating and Reporting Adverse Events and Serious Adverse Events

### A. GENERAL INSTRUCTIONS

1. AEs will be recorded after the first dose of study drug is administered.
2. AEs will be reported on an AE CRF.
3. Report the severity of the event following the guidance in section B below.
4. Report the relatedness of the event to the investigational product administration according to the guidance in section C.

### B. DEFINITIONS – SEVERITY OF EVENTS

Mild:	Awareness of symptom, but easily tolerated.
Moderate:	Discomfort enough to cause interference with usual activity.
Severe:	Incapacitating with inability to work or do usual activity.

### C. DEFINITIONS – RELATEDNESS OF EVENTS

The study Investigator is responsible for defining, in his/her best judgment, the relationship of the AE/SAE to the investigational product. The degree of certainty for which the AE/SAE is attributed to the investigational product or alternative causes (*e.g.*, natural history of the underlying disease, concomitant therapies, *etc.*) should be determined by how well the experience can be understood in terms of one or more of the following:

- ***Exposure:*** Is there evidence that the participant was actually exposed to the investigational product?
- ***Timing of the administration of investigational product:*** Did the AE/SAE follow in a reasonable temporal sequence from administration of the investigational product?
- ***Consistency with investigational product safety profile:*** Known pharmacology and toxicology of the investigational product in animals and man; reaction of similar nature having been previously described with the investigational product.
- ***Alternative explanations*** for the adverse event such as concomitant medications, concurrent illness, non-medicinal therapies, diagnostic tests, procedures or other confounding findings.
- ***Response to discontinuation*** of the investigational product.

Terms and definitions to be used in assessing the investigational product relationship to the AE/SAE are:

- **Unknown:**  
Use this category only if the cause of the AE/SAE is not possible to determine.
- **Definitely Not Related:**  
The participant did not receive investigational product, the temporal sequence of the AE/SAE onset relative to administration of the investigational product is not reasonable, or there is another obvious cause of the AE/SAE.
- **Unlikely Related:**  
There is evidence of exposure to the investigational product or there is another more likely cause of the AE/SAE.
- **Possibly Related:**  
There is evidence of exposure to the investigational product, the temporal sequence of the AE/SAE onset relative to administration of the investigational product is reasonable, but the AE/SAE could have been due to another equally likely cause.
- **Probably Related:**  
There is evidence of exposure to the investigational product, the temporal sequence of the AE/SAE onset relative to administration of the investigational product is reasonable, and the AE/SAE is more likely explained by the investigational product than by any other cause.
- **Definitely Related:**  
There is evidence of exposure to the investigational product, the temporal sequence of the AE/SAE onset relative to administration of the investigational product is reasonable, the AE/SAE is more likely explained by the investigational product than by any other cause, and the AE/SAE shows a pattern consistent with previous knowledge of the investigational product or investigational product class.

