### 9.12 Study Stopping Criteria

The study will be halted from further enrollment if any of the following criteria are met at any point during the study:

- Four participants experience a severe AE, such as significant neurological or psychiatric events (*e.g.*, psychosis) or behavioral manifestations of cocaine toxicity
- Two participants experience a similar SAE that is not clearly unrelated to study drug or cocaine
- Two severe AEs related to cocaine toxicity
- Two participants fulfill the following ECG criteria based on the mean of triplicate measures ( $\geq 1$  minute apart), that will be completed once the first ECG demonstrates a prolonged interval: QTcF  $\geq 500$  msec or uncorrected QT interval of  $>600$  msec.

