## 10 ASSESSMENT METHODS

### 10.1 Adverse Events

Reports of AEs will be elicited by a verbal probe (*e.g.*, “How are you feeling?”) administered starting with the first cocaine screening infusion on Day -2. Any events spontaneously reported by the participant or observed by the investigative staff will also be recorded. AEs will be assessed for severity and relationship to the study drug in accordance with the criteria in [APPENDIX B](#).

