## **7.4 Primary Outcome Measures**

### **7.4.1 Adverse Events**

AE data will be compiled for the SXC-2023 and placebo groups and presented as summary statistics for the safety population. A new illness, symptom, sign or clinically significant clinical laboratory abnormality or worsening of a pre-existing condition or abnormality is considered an AE. AEs will be coded using the most recent version of the Medical Dictionary for Regulatory Activities (MedDRA) preferred terms and will be grouped by system, organ, class (SOC) designation. Listings of each individual AE including start date, stop date, severity, relationship, outcome, and duration will be provided.

The number (and percentage) of participants with treatment emergent adverse events (events started after the first dose of study medication or events present prior to start of double-blind treatment but increased in severity based on preferred term) will be summarized in the following ways:

- by treatment, primary system organ class and preferred term.

- by treatment, primary system organ class, preferred term, and maximum severity.

Separate summaries will be provided for related (definitely, probably, or possibly) adverse events for treatment emergent adverse events and serious adverse events (separately for SXC-2023 and cocaine). Listings of all adverse events and serious adverse events will be provided. Additionally, a listing will be provided for adverse events leading to death, withdrawal or discontinuation.

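### Appendix B describes one relatedness grade against an unsettled 'investigational product', so the protocol describes no source variable for the SAP's separate SXC-2023 and cocaine related-AE summaries

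*Protocol*

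**What the plan says.** Appendix B, part A instructs: "Report the relatedness of the event to the investigational product administration according to the guidance in section C". Protocol Section 10.1 states the target differently: "AEs will be assessed for severity and relationship to the study drug in accordance with the criteria in" Appendix B. Section 12.4.1 also reports relationship to study drug.

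Part C gives six terms and leaves the choice to the investigator's judgment. Three of them matter here:

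- Definitely Not Related is met by any one of three alternatives: no receipt of the product, an unreasonable time sequence, "or there is another obvious cause of the AE/SAE".
- Unlikely Related reads: "There is evidence of exposure to the investigational product or there is another more likely cause of the AE/SAE".
- Possibly Related needs exposure and a reasonable time sequence, "but the AE/SAE could have been due to another equally likely cause".

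The alternative explanations to be weighed are listed as "such as concomitant medications, concurrent illness, non-medicinal therapies, diagnostic tests, procedures or other confounding findings". The list names neither the cocaine challenge nor an interaction with it.

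SAP 7.4.1 plans separate summaries of related events (definitely, probably or possibly) for treatment-emergent events and "serious adverse events (separately for SXC-2023 and cocaine"). Protocol Section 9.12 includes the criterion "Two severe AEs related to cocaine toxicity".

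**The concern.** The primary objective is to detect an interaction between SXC-2023 and intravenous cocaine, and AEs are a primary endpoint. The scale in Appendix B sets causes against each other: an event is due to the product or to something else. The event of most interest here has both causes, being an expected cocaine effect made stronger or longer by SXC-2023. The scale has no place for it.

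Such borderline cases will not be rare. In the cocaine and lorcaserin interaction study described in Protocol Section 2.2.2.2, cocaine-related euphoric mood occurred in 25 of 26 participants (96%) and tachycardia in 6 of 26 (23%). Events with cocaine as an evident cause will be routine on infusion days. At stake is whether the related-event tables can be read as statements about SXC-2023, about cocaine, or about neither.

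**Working it through.** No sample size, error rate or margin is involved, so the check sets the texts side by side.

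**1. What is the grade against?**

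- Towards SXC-2023 only: the synopsis names SXC-2023 as the study drug, and the stopping criteria in 9.10 and 9.12 name study drug and cocaine as alternatives.
- Towards including cocaine: Section 8, Investigational Product, has subsections for SXC-2023, placebo and cocaine. The synopsis row on study drugs and dosing lists cocaine. SAP 7.1 speaks of an infusion of study drug, and SAP 7.3 counts cocaine sessions as study drug exposure.

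The documents support both readings and settle neither.

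**2. Reading A: the product is SXC-2023.** Take tachycardia after the 40 mg infusion on Day 9, worse than in the same participant's Day 2 session, in the SXC-2023 arm.

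- Definitely Not Related is open, because the cocaine just given is an obvious cause.
- Unlikely Related is met, by exposure alone.
- Possibly Related is open if the investigator thinks the two causes equally likely.

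The text supports at least these three grades for one event. Two fall outside the SAP's related set and one falls inside.

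**3. Reading B: the product includes cocaine.** The same event can be graded Probably or Definitely Related on the strength of the cocaine alone. So can an ordinary cocaine effect in the placebo arm. The grade does not identify the agent.

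**4. Required against described.** SAP 7.4.1 needs 2 agents × 2 event classes (treatment-emergent and serious) = 4 related-event summaries. The protocol describes 1 grade with no agent label, and SAP 7.4.1 names no variable. Under neither reading does that one grade supply both agents' summaries.

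**5. Unlikely Related.** With 'or', exposure is sufficient. Possibly, Probably and Definitely Related all require exposure, so every event in those grades also meets Unlikely Related. With 'and', the grade requires exposure together with a more likely other cause, and the overlap through exposure alone disappears.

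**6. Term lists.** Part C has six terms: Unknown, Definitely Not, Unlikely, Possibly, Probably and Definitely Related. The initial SAE report in part E has five: not, unlikely, possibly and probably related, and related. Unknown has no counterpart there. SAP 7.4.1 counts three of the six as related and does not mention Unknown.

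**7. Where the grade is used.** It feeds the related-event summaries. It also enters the 7-day FDA reporting condition in Appendix B, which requires the SAE to be at least possibly related to the investigational product. It is not used in the SAP 7.4.1 tables of all treatment-emergent events by arm, or by maximum severity, nor in the HR and BP analyses of SAP 7.4.2.

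**The case against.** The strongest case on the other side is that this concerns supplementary tables only, and most of that case stands.

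- A reader might infer that causality is recorded only once and that the SAP tables cannot be built. The documents do not show this. The AE CRF is not among them, and the SAP's plan to report by agent suggests that two fields may exist. What can be said is that the protocol describes no source for the second attribution. If the CRF has two fields, Appendix B still gives no rule for completing the cocaine one.
- A reader might infer that potentiated cocaine effects vanish from the primary endpoint and bias it towards no interaction. They do not. The endpoint is AEs, not related AEs. All treatment-emergent events are tabulated by randomised arm and by maximum severity whatever the grade. HR and BP are compared by ANCOVA adjusted for the baseline session, with no causality judgment.
- A reader might infer that such an event will be graded not related. The text only permits that. The investigator may choose Possibly Related, and the outcome arises only under Reading A.
- A reader might infer that the cocaine-toxicity stopping criterion cannot be applied. Nothing ties that criterion to the Appendix B grade, and it can be applied by clinical judgment. The medical monitor also tracks AE trends and advises on SAE relatedness (Section 11.5).

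The objection does not dispose of the point. Definitions followed literally give wrong or inseparable entries in tables that the SAP has committed to.

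**Conclusion.** The concern holds in a limited form. The protocol describes one relatedness grade against a term whose meaning shifts between sections. Under one meaning, a cocaine effect worsened by SXC-2023 can be graded Definitely Not Related. Under the other, the agent is not identified. The agent-specific summaries in SAP 7.4.1 therefore have no described source variable. The wording of Unlikely Related and the five-against-six term lists are separate drafting faults visible on the page.

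The reach is the related treatment-emergent and serious AE summaries, together with decisions that use the grade, such as 7-day reporting. The comparison of all AEs by arm and the cardiovascular analyses stand as planned.

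No count of misgraded events can be derived. The 96% and 23% from the lorcaserin study show how common cocaine-attributed events are, not how often they would be misgraded. The conclusion rests on the protocol and SAP text alone; a CRF with two causality fields would remove the source-variable gap but not the faults in the definitions. This should be corrected, but it does not threaten the trial's main comparison.

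**What to change.** - **Define the term.** State in Section 8 and Appendix B what investigational product and study drug mean, and use the terms consistently in the protocol and SAP.
- **Two grades.** Record relatedness to SXC-2023/placebo and relatedness to cocaine separately, on the same scale, in Appendix B and on the AE CRF.
- **Joint causes.** State that a plausible cocaine cause does not by itself make an event not related to SXC-2023.
- **Unlikely Related.** Change 'or' to 'and'.
- **Term lists.** Align the SAE report list in part E with the six terms in part C.
- **SAP 7.4.1.** Name both variables, and say which one feeds each related-event summary.
- **Sections 9.10 and 9.12.** The sponsor should reconcile their attribution wording with Appendix B. No change to the stopping criteria is proposed here.

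The cost is one or two CRF fields and short text edits, with no extra visits or procedures. The small downside is that more events will be listed as possibly related.
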